- Patients who are incapacitated and/or uncooperative during the treatment phase
- The treatment of at-risk groups is inadvisable

All APTUS cannulated screws systems have a specific color coding: APTUS 5.0 dark blue, APTUS 7.0 turquoise. Special implant screws have their own color. To ensure that the lengths of the screws to be used are measured correctly, only original Medartis K-wires of 250 mm in length may be used. The K-wires should be selected depending on the screw size: Ø 1.6 mm for APTUS 5.0 and Ø 2.2 for APTUS 7.0.

Study objectives:

The objectives of presented prospective multicenter study are to:

- Determine intraoperative and perioperative complications;
- Assess osseous union following arthrodesis;
- Assess postoperative alignment including the cases with possible malalignment/malunion;
- Assess postoperative pain relief at the time of mid-term follow-up;
- Assess the patients' mid-term functional outcome and level of patient satisfaction;
- Determine the rate of secondary surgical procedures for any reason including hardware removal.

Hypothesis 1:

The rate of intraoperative complications is very low.

Specific aim 1:

All intraoperative complications including injury of neurovascular structures and/or tendons will be prospectively documented. All intraoperative technical difficulties (for example, breakage of the screw) will be prospectively documented. The rate of the intraoperative complications will be calculated by an independent observer.

Hypothesis 2:

The rate of perioperative complications is very low.

Specific aim 2:

All perioperative complications including wound healing problems and/or superficial/deep infection and/or deep vein thrombosis will be prospectively documented. The rate of the perioperative complications will be calculated by an independent observer.

Hypothesis 3:

The rate of delayed osseous union or non-union is very low and is comparable with the lower range published in the current literature.

Specific aim 3:

The osseous union will be measured by Duke's independent radiologist. Fusion will only be measured in the patients 6 week radiograph, 3 month radiograph, and 6 month CT scan and radio graph. No additional measurements of fusion will need to be taken, unless the patient still has a non-union at 6 months. At that time the radiologist will go ahead and measure for fusion at 1 and 2 year post -op.

Hypothesis 4:

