The fixation of a subtalar, double, or triple arthrodesis will result in neutral hindfoot alignment stable over the time.

Specific aim 4:

The hind foot alignment will be measured by Duke's Independent radiologist. The subject's radiographs at 6 weeks, 3 months, 6 months, 1 year and 2 years post operatively will be used to make these measurements.

Hypothesis 5:

The subtalar, double, or triple arthrodesis will result in substantial pain relief.

Specific aim 5:

The patients will rate their pain on a visual analogue scale (VAS) from 0 points (no pain) to 10 points (maximal pain) preoperatively and postoperatively at the 3 month, 6 month, 1 year, and 2 year follow-up visits. The intra-individual changes over the time will be statistically analyzed.

Hypothesis 6:

The subtalar, double, or triple arthrodesis will result in substantial functional improvement.

Specific aim 6:

The functional status will be assessed using the American Orthopaedic Foot and Ankle Society (AOFAS) hindfoot score and Foot & Ankle Disability Index (FADI) score preoperatively and postoperatively at the 3 month, 6 month, 1 year, and 2 year follow-up visits. The intra-individual changes over the time will be statistically analyzed.

Hypothesis 7:

The rate of secondary surgical procedures for any reason including hardware removal.

Specific aims 7:

All postoperative complications requiring any secondary surgical procedures including hardware removal will be prospectively documented. The rate of the perioperative complications will be calculated by an independent observer.

REFERENCES

- (1) Ryerson E. Arthrodesing operations of the feet. *J Bone Joint Surg Am* 1923; 5:453-471.

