All patients will be seen preoperatively and postoperatively in the outpatient clinic by their provider or their provider's physician assistant. The clinical examination involves careful preoperative and postoperative assessment of ankle alignment, ankle stability, and ankle range of motion. Ankle range of motion will be determined with a goniometer placed along the lateral border of the leg and foot. All goniometer measurements will be performed in the weight-bearing position, comparable with the method described by Lindsjö et al. (18). The patients will rate their pain on a visual analogue scale (VAS) from 0 points (no pain) to 10 points (maximal pain) (19). Patients will also indicate their satisfaction with the procedure using modified Coughlin rating for category scale (appendix 1): very satisfied, satisfied, partially satisfied, and not satisfied (20). Patients' function status will be assessed using the American Orthopaedic Foot and Ankle Society (AOFAS) hindfoot score (appendix 2) (21). Additionally, the Foot & Ankle Disability Index (FADI) score will be calculated (appendix 3) (22). Patients will be asked to complete the study-related questionnaires during their routine clinic visits. If a patient is unable to return to clinic, however, the questionnaires may be completed with a study team member over the phone or mailed to the patient for completion. The documentation process is summarized in the table 3 below.

Surgical assessment:

A case report form will be provided in the operating room by a member of the study team to document any operative adverse events, bone graft used (if used), deformity correction, tendo-Achilles lengthening or tendon transfer(s) as well as product category and lot numbers.

Radiographic assessment:

All affected ankles will be evaluated preoperatively and postoperatively using a four film series of conventional radiographs including anteroposterior and lateral views of the foot, mortise view of the ankle, and Saltzman view (23) of the hindfoot. Only weight-bearing radiographs of the foot and ankle will be acceptable because non-weight-bearing radiographs are often misleading (24-26). Furthermore, the standing position may help to standardize the radiograph technique, allowing more reliable comparison of interindividual and intraindividual radiographs. The radiographs should include a sphere calliper in order to hold standardize radiographs taken.

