The full interpretation of these radiographs and computed tomography scans are to be made by Duke's radiology team as standard of care. There will be one Duke independent radiologist who will only make measurements of the osseous union fusion and hind foot alignment. This independent radiologist will access the subject's radiographs and CT scan from PACS and record the measurements in an excel spreadsheet that is saved on the DHTS server.

Selection of Subjects

Patients will be identified in the clinic by an attending orthopaedic foot and ankle surgeon or his physician assistant based on clinical exam and radiographic findings. Inclusion criteria include anyone over age 18 who has ankle and subtalar arthritis and has failed nonoperative management. Typically, these patients have multiple medical comorbidities and therefore the only exclusion criteria will be patients who are not healthy enough to undergo surgery. Patients of all racial, religious, and cultural backgrounds will be included in this study.

Indications:

- Primary subtalar, double, or triple arthrodesis
- Rheumatoid or posttraumatic osteoarthritis of the hindfoot with involvement of subtalar, talonavicular, and calcaneocuboid joints (2;12).
- Symptomatic rigid pes planovalgus et abductus with end-stage posterior tibial tendon dysfunction (for example, grade IV) (4;13-15).
- Neuromuscular disease mediated hindfoot deformities (16).
- Tarsal coalitions (17).
- Indication for calcaneocuboid arthrodesis: severe degenerative changes in the calcaneocuboid joint and/or severe abductus deformity of the forefoot.
- Between the age 18-75

Contraindications:

- Acute or chronic infection.
- Poor vascular status of the lower leg (relative contraindication for double arthrodesis through a single medial approach).
- Women that are pregnant.

Subject Recruitment and Compensation

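### The weight-bearing-only rule makes no exception for fusion films, so a patient who cannot stand can lose the 6-week or 3-month fusion reading

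*Combined protocol and SAP*

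**What the plan says.** The Radiographic assessment section sets the imaging for the whole study: "All affected ankles will be evaluated preoperatively and postoperatively using a four film series of conventional radiographs", taken in four named views. It then adds the acceptance rule: "Only weight-bearing radiographs of the foot and ankle will be acceptable because non-weight-bearing radiographs are often misleading (24-26". A second reason follows, that standing helps to standardise films for comparison between and within patients. The rule is not limited to a visit or to a measurement.

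Two measurements use these films. For fusion, Specific aim 3 says "Fusion will only be measured in the patients 6 week radiograph, 3 month radiograph, and 6 month CT scan and radio graph", and then "No additional measurements of fusion will need to be taken, unless the patient still has a non-union at 6 months", in which case "the radiologist will go ahead and measure for fusion at 1 and 2 year" after surgery. For hindfoot alignment, Specific aim 4 says "The subject's radiographs at 6 weeks, 3 months, 6 months, 1 year and 2 years post operatively will be used to make these measurements".

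The fusion readings serve Hypothesis 3: "The rate of delayed osseous union or non-union is very low and is comparable with the lower range published in the current literature". On how films reach the reader, the plan says only that "This independent radiologist will access the subject's radiographs and CT scan from PACS and record the measurements in an excel spreadsheet".

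The documents do not say what happens to a film taken without weight-bearing, how many patients are expected to be unable to stand, what time point separates delayed from normal union, or how a missing fusion reading is handled. Clinical assessment gives a telephone or postal fallback for the questionnaires. There is no fallback for a patient who cannot stand for a film.

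**The concern.** One acceptance rule governs two measurements, but the first reason given for it concerns only one of them. Judged by their titles, the three references cited for it deal with hindfoot pain on weight-bearing imaging, lower-limb alignment and hindfoot alignment. Nothing in the plan says that a non-standing film misleads about union.

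A patient may be unable to stand on the foot because of pain, wound trouble or poor healing. If so, a missing fusion reading could be related to the outcome being read. At stake are the 6-week and 3-month data. These are the only fusion readings before 6 months, and so the only basis for saying when union occurred or for counting delayed unions. Hypothesis 3 combines delayed union and non-union in one rate, so a gap in the early readings feeds into it.

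**Working it through.** **The plan's own figures.** The plan gives no figure for missing readings or for union. Its only related number is 50 patients for a precision of ±7.5% and ±10% (Design & Procedures), without a confidence level or assumed rates. Taking 95% confidence and the Wald half-width 1.96 × √(p(1−p)/50), p = 8% gives ±7.5 points and p = 15% gives ±9.9 points. The figures are thus consistent with rates near 8% and 15%, but those rates are back-solved and not stated. They serve below only as a yardstick.

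**Which readings the rule reaches.**

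| Visit | Fusion read on | Under the rule? | If the patient cannot stand |
|---|---|---|---|
| 6 weeks | radiograph | yes | no fusion reading |
| 3 months | radiograph | yes | no fusion reading |
| 6 months | CT and radiograph | radiograph only | CT reading remains |
| 1 and 2 years, non-unions at 6 months only | modality not named in aim 3; radiographs are the only imaging named for these visits | yes, if radiographs | later healing may go unseen; the patient is already a known non-union |

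**Missing readings dropped.** Let p be the true share not united at an early visit, and m1 and m0 the shares of un-united and united patients without an acceptable film. All three are assumptions. The observed rate is

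p(1−m1) / [p(1−m1) + (1−p)(1−m0)].

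With p = 0.15:

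- m1 = 0.30, m0 = 0.10: 0.105 / 0.870 = 12.1%
- m1 = 0.40, m0 = 0.10: 0.090 / 0.855 = 10.5%, with 50 × 0.855 ≈ 43 readable patients
- m1 = 0.50, m0 = 0.05: 0.075 / 0.8825 = 8.5%

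The same three pairs give 5.5% to 8.0% for a true 10%, and 11.6% to 16.3% for a true 20%. The middle case at 15% shifts the rate by 4.5 points, against the plan's ±7.5 and ±10.

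These pairs all assume strongly unequal missingness. In the middle case the not-united risk among patients without a film is 0.060 / 0.145 = 41%, about 3.9 times the 10.5% among those with one.

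**Other assumptions.**

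- Equal missingness (m1 = m0): the factors cancel and the observed rate is 15%. No bias.
- Missing counted as not united: the rate becomes p + (1−p)m0. This is 0.15 + 0.85 × 0.10 = 23.5% for the first two pairs and 0.15 + 0.85 × 0.05 = 19.3% for the third. The bias is upward.

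**A second parametrisation.** Let f be the share of patients losing the reading and RR their not-united risk relative to the rest. With missing readings dropped, the observed rate is p / (1 − f + f × RR). At p = 10% and f = 10%:

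| RR | Observed | Shift (points) |
|---|---|---|
| 0.5 | 0.10 / 0.95 = 10.5% | +0.5 |
| 1 | 0.10 / 1.00 = 10.0% | 0 |
| 2 | 0.10 / 1.10 = 9.1% | −0.9 |
| 3 | 0.10 / 1.20 = 8.3% | −1.7 |

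Over p from 5% to 15% and f from 5% to 20%, the shift is −0.2 to −2.5 points at RR 2, −0.5 to −4.3 at RR 3, and +0.1 to +1.7 at RR 0.5. If lost readings are instead counted as not united, a true 10% with f = 10% becomes 17.5% (RR 3: 0.0833 × 0.9 + 0.1) to 19.5% (RR 0.5: 0.1053 × 0.9 + 0.1).

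**The case against.** The strongest reply is that the plan describes no step at which a film is discarded. The rule can be read as an instruction on how films are to be taken, and the independent radiologist simply opens whatever is in PACS. That is a possible reading. It does not create an exception, however: a film that is not acceptable has no stated use, and on the lenient reading a single reader decides film by film without a rule. Either way the text needs settling.

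A second reply is that standardisation may matter for serial fusion readings too. The plan's use of CT at 6 months does not show that non-standing plain films are adequate for reading union, since CT is a different modality. This stands. The contents of the cited references cannot be checked here either. It is why the fix asks for diagnostic quality and a record of loading status, and why some loss of standardisation is counted as a cost.

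A third reply is that the underlying gaps are the missing definition of delayed union and the missing rule for absent readings. That is also fair. Limiting the weight-bearing rule does not fill those gaps, but it reduces how often they matter.

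**Conclusion.** The point holds as an avoidable source of missing early fusion readings. The rule, read literally, covers the 6-week, 3-month and 6-month radiographs. The 6-month CT limits the damage at that visit, which leaves mainly the 6-week and 3-month readings exposed.

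A reader might infer more, in three ways that the documents do not support.

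- **That patients who cannot stand go without any fusion assessment.** They do not: the 6-month CT lies outside the rule, so non-union at 6 months, which triggers the later readings, stays observable.
- **That the delayed-union rate is biased low.** This needs inability to stand to go with slower healing, and missing readings to be dropped. The first is plausible and the second a likely default, but neither is stated. Under both, an assumed true 15% is observed as 8.5% to 12.1%. With equal missingness the bias is zero. If missing readings count as not united, or a patient first seen united at 6 months is classed as delayed, it is upward.
- **That films lost at 1 and 2 years flatter Hypothesis 3.** Patients read then are already known non-unions. A lost film could only hide later healing and would not lower the combined rate.

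The direction is therefore plausible but not established, and every size given here rests on assumed inputs. The change is worth making as a cheap improvement, because it prevents missing readings whichever way the bias would run.

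**What to change.** In Radiographic assessment, limit the rule to alignment, for example: *Hindfoot alignment is measured on weight-bearing films only. Fusion is read on any film of diagnostic quality, weight-bearing or not, and the loading status is recorded.* Where no standing film was taken, record the reason. Report the number of missing fusion readings and missing alignment readings at each visit beside the results.

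The cost is one sentence in the protocol and one field on the reading form. The downside is that some fusion films will be less standardised in projection; the recorded loading status lets the analysis show how many. The alignment measurement keeps its present standard.
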